4.0 Background*

4.1 *Provide the scientific or scholarly background, rationale, and significance of the research based on the existing literature and how it will contribute to existing knowledge. Describe any gaps in current knowledge. Include relevant preliminary findings or prior research by the investigator.*

Response:

Vulvodynia is a heterogeneous group of clinical conditions defined by the [International Society for the Study of Vulvovaginal Disease](#) as chronic vulvar discomfort or pain, characterized by burning, stinging, irritation or rawness of the female genitalia [1]. The true prevalence is unknown but is estimated at 9-12% of the adult female population, with up to 2 million women affected. These chronic conditions cause significant burden in terms of quality of life and relationship dysfunction, especially for women with provoked vestibulodynia (pain at the opening of the vagina (“vestibule”) with vaginal penetration or attempted vaginal penetration) which interferes with normal sexual function [2]. This is a “hidden” women’s issue that is under-reported and under-treated because it causes embarrassment and feelings of inadequacy. The clinical management of localized, provoked vulvodynia has been disorganized and somewhat arbitrary [3]. Studies suggest that most women see a variety of providers over the course of months to years before the condition is diagnosed correctly. Diagnosis of these conditions is based on clinical picture, absence of other causes, and physical exam. During the exam, a cotton-tipped swab is used to assess for areas of tenderness and the patient is asked to rate her level of pain on a Likert scale. This has been the standard of care for many years, but reproducibility has not been assessed. In addition, monitoring response to therapy is also very subjective. Even return to sexual activity is not a reliable indicator of patient’s pain, since many women will continue to engage in sexual activity to avoid relationship discord. We have been developing a novel medical technique for the diagnosis and classification of vulvodynia. The technique will quantitatively measure mechanical sensitivity to touch/pressure simultaneously with thermal indicators of inflammation. The technique builds on current methodology used in assessment and knowledge about the known pathophysiology of the disorder. Through this combination of measurements, we plan to expand the diagnostic tools used in patient care as well as on the classification of this heterogeneous disorder.

4.2 *Include complete citations or references.*

Response:

5.0 Study Design*

5.1 *Describe and explain the study design (e.g. case-control, cross-sectional, ethnographic, experimental, interventional, longitudinal, observational).*

Response:

Prospective study of women with vulvodynia and normal controls. We plan to evaluate a novel technique that quantifies both pain intensity and records thermographic changes of the vulva in women with a clinical diagnosis of provoked vulvodynia and normal controls. The study subjects will have a new or prior diagnosis of provoked vulvodynia and will be invited to participate in this evaluation. Women with prior diagnosis of vulvodynia will be symptomatic and untreated at the time of assessment. Control subjects will be unaffected women presenting for routine care who do not have vulvar pain or other active vulvar or vaginal disorder as these may interfere with thermographic mapping.

6.0 Study Intervention/Investigational Agent

6.1 *Describe the study intervention and/or investigational agent (e.g., drug, device) that is being evaluated.*

Response: Thermographic imaging of the vulva combined with subjective pressure sensitivity assessments, overlaid onto a pain map of the vulva.

6.2 *Drug/Device Handling: If the research involves drugs or device, describe your plans to store, handle, and administer those drugs or devices so that they will be used only on subjects and be used only by authorized investigators.*

- *If the control of the drugs or devices used in this protocol will be accomplished by following an established, approved organizational SOP (e.g., Research Pharmacy SOP for the Control of Investigational Drugs, etc.), please reference that SOP in this section.*

Response:

NA

6.3 *If the drug is investigational (has an IND) or the device has an IDE or a claim of abbreviated IDE (non-significant risk device), include the following information:*

- *Identify the holder of the IND/IDE/Abbreviated IDE.*
- *Explain procedures followed to comply with sponsor requirements for FDA regulated research for the following:*

FDA Regulation	Applicable to:		
	IND Studies	IDE studies	Abbreviated IDE studies
21 CFR 11	X	X	
21 CFR 54	X	X	
21 CFR 210	X		
21 CFR 211	X		
21 CFR 312	X		
21 CFR 812		X	X
21 CFR 820		X	

Response:

The device has no contact with the patient, it takes IR and photo images remote from the patient, and so is not subject to IDE.

7.0 Local Number of Subjects

7.1 *Indicate the total number of subjects that will be enrolled or records that will be reviewed locally.*

Response: 60 (sixty)

7.2 *If applicable, indicate how many subjects you expect to screen to reach your target sample (i.e. your screen failure rate).*

Response: 100

7.3 *Justify the feasibility of recruiting the proposed number of eligible subjects within the anticipated recruitment period. For example, how many potential subjects do you have access to? What percentage of those potential subjects do you need to recruit?*

Response: The PI sees an average of 5 new patients per month diagnosed with vulvodynia and has many established patients who can be assessed when they come in for follow-up. For affected women, the goal would be to recruit close to 100% of them. The Ob/Gyn practice is an eight-person general Ob/Gyn practice that sees 50-70 women per week for routine gynecologic care. Only a small fraction of these women will need to be recruited.

8.0 Inclusion and Exclusion Criteria*

8.1 *Describe the criteria that define who will be **included** in your final study sample.*

NOTE: This may be done in bullet point fashion.

Response:

Women > 18 years of age

Women seeking care for vulvar pain

Controls: Women seeking routine gynecologic care

8.2 *Describe the criteria that define who will be **excluded** from your final study sample.*

NOTE: This may be done in bullet point fashion.

Response:

Women < 18 years of age

Pregnancy

Women with vulvar or vaginal disorder other than pain

8.3 *Indicate specifically whether you will include any of the following special populations in your study using the checkboxes below.*

NOTE: Members of special populations may not be targeted for enrollment in your study unless you indicate this in your inclusion criteria.

Response:

- Adults unable to consent
- Individuals who are not yet adults (infants, children, teenagers)
- Pregnant women
- Prisoners

8.4 *Indicate whether you will include non-English speaking individuals in your study. Provide justification if you will exclude non-English speaking individuals.*

*In order to meet one of the primary ethical principles of equitable selection of subjects, non-English speaking individuals may **not** be routinely excluded from research as a matter of convenience.*

In cases where the research is of therapeutic intent or is designed to investigate areas that would necessarily require certain populations who may not speak English, the researcher is required to make efforts to recruit and include non-English speaking individuals. However, there are studies in which it would be reasonable to limit subjects to those who speak English. Some examples include pilot studies, small unfunded studies with validated instruments not available in other languages, studies with numerous questionnaires, and some non-therapeutic studies which offer no direct benefit.

Response:

Non-English speakers are not eligible for inclusion in the study. This is a non-therapeutic study which will offer no direct benefit.

9.0 Vulnerable Populations*

If the research involves special populations that are considered vulnerable, describe the safeguards included to protect their rights and welfare.

NOTE: You should refer to the appropriate checklists, referenced below, to ensure you have provided adequate detail regarding safeguards and protections. You do not, however, need to provide these checklists to the IRB.

9.1 *For research that involves pregnant women, safeguards include:*

NOTE CHECKLIST: Pregnant Women (HRP-412)

Response:

N/A: This research does not involve pregnant women.

9.2 *For research that involves neonates of uncertain viability or non-viable neonates, safeguards include:*

NOTE CHECKLISTS: Non-Viable Neonates (HRP-413), or Neonates of Uncertain Viability (HRP-414)

Response:

N/A: This research does not involve non-viable neonates or neonates of uncertain viability.

9.3 *For research that involves prisoners, safeguards include:*

NOTE CHECKLIST: Prisoners (HRP-415)

Response:

N/A: This research does not involve prisoners.

9.4 *For research that involves persons who have not attained the legal age for consent to treatments or procedures involved in the research (“children”), safeguards include:*

NOTE CHECKLIST: Children (HRP-416)

Response:

N/A: This research does not involve persons who have not attained the legal age for consent to treatments or procedures (“children”).

9.5 *For research that involves cognitively impaired adults, safeguards include:*

NOTE CHECKLIST: Cognitively Impaired Adults (HRP-417)

Response:

N/A: This research does not involve cognitively impaired adults.

9.6 *Consider if other specifically targeted populations such as students, employees of a specific firm, or educationally or economically disadvantaged persons are vulnerable. Provide information regarding their safeguards and protections, including safeguards to eliminate coercion or undue influence.*

Response:

N/A

10.0 Eligibility Screening*

10.1 *Describe screening procedures for determining subjects' eligibility. Screening refers to determining if prospective participants meet inclusion and exclusion criteria.*

 *Include all relevant screening documents with your submission (e.g. screening protocol, script, questionnaire).*

Response: Exclusion criteria include pregnancy, age < 18 years, and active vulvar and vaginal disorder other than pain, to be assessed in two ways: during the recruitment interview and at the time of the exam.

N/A: There is no screening as part of this protocol.

11.0 Recruitment Methods

N/A: This is a records review only, and subjects will not be recruited. NOTE: If you select this option, please make sure that all records review procedures and inclusion/exclusion screening are adequately described in other sections.

11.1 *Describe when, where, and how potential subjects will be recruited.*

NOTE: Recruitment refers to how you are identifying potential participants and introducing them to the study. Include specific methods you will use (e.g. searching charts for specific ICD code numbers, Research Participant Groups, posted advertisements, etc.).

Response: Women will be approached by the PI when they come to the clinical suite for evaluation of vulvar pain (subjects). Women will be approached by their own provider prior to routine annual exam to ask permission for the PI or study coordinator to discuss the study with them (controls). Some women will be called by the study coordinator in advance of their scheduled clinic visit and invited to participate in the study to save time on the day of the visit. The consent form will be discussed with them and then signed when they arrive for their clinic visit.

11.2 *Describe how you will protect the privacy interests of prospective subjects during the recruitment process.*

NOTE: Privacy refers to an individual's right to control access to him or herself.

Response: Women will be approached by telephone prior to their study visit or in private once they have been ushered into an exam room by clinical staff. If a patient agrees to consider recruitment, study staff will then explain the study and patient's participation in a private room.

11.3 Identify any materials that will be used to recruit subjects.

NOTE: Examples include scripts for telephone calls, in person announcements / presentations, email invitations.

 For advertisements, include the final copy of printed advertisements with your submission. When advertisements are taped for broadcast, attach the final audio/video tape. *NOTE: You may submit the wording of the advertisement prior to taping to ensure there will be no IRB-required revisions, provided the IRB also reviews and approves the final version.*

Response: N/A – we are using a direct recruitment method.

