1.0 Study Summary

Study Title	Objective Assessment of Pain Thresholds in Women with Vulvodynia
Study Design	Clinical Trial
Primary Objective	Develop annotated pain maps showing region and size of area sensitive to mechanical stimulus. The pain maps will be created by combining IR images, photographs, and clinical input, and will be correlated with patient co-morbidities.
Secondary Objective(s)	a-Determine changes in the location and size of sensitive regions following various conventional clinical interventions for vulvodynia. b-Develop a large, information-rich database of annotated pain maps from patients, and use Artificial Intelligence to identify patterns and trends.
Research Intervention(s)/ Investigational Agent(s)	Infrared imaging of the vulva and assessment of pain intensity using cotton-tipped swab.
IND/IDE #	N/A
Study Population	Women with vulvodynia and healthy controls
Sample Size	60 women (30 in each group)
Study Duration for individual participants	One day 1 hour

Study Specific Abbreviations/ Definitions	
--	--

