3.0 Scientific Endpoints*

3.1 *Describe the scientific endpoint(s), the main result or occurrence under study.*

NOTE: Scientific endpoints are outcomes defined before the study begins to determine whether the objectives of the study have been met and to draw conclusions from the data. Include primary and secondary endpoints. Some example endpoints are: reduction of symptoms, improvement in quality of life, or survival. Your response should not be a date.

Response:

Thermographic evidence of inflammation in the areas of pain sensitivity in women with provoked vulvodynia compared to normal controls.

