12.0 Procedures Involved*

12.1 Provide a description of **all research procedures or activities** being performed and when they are performed once a subject is screened and determined to be eligible. Provide as much detail as possible.

NOTE: This should serve as a blueprint for your study and include enough detail so that another investigator could pick up your protocol and replicate the research. For studies that have multiple or complex visits or procedures, consider the addition of a schedule of events table in in your response.

Response:

All procedures will be performed on the same day as screening and consent and are expected to take 30-60 minutes. An annotated pain map of the vulva will be created based on subjective assessment of pain, and thermographic imaging.

- A. Images and Thermographic readings will be taken with an infrared camera prior to any physical contact with the vulva of the patient other than by placing a calibrated paper drape circumferentially on the vulva outside of the area of interest. The drape will be calibrated to maintain pain map/image size comparison between patients.
- B. Subjective pain at several predetermined loci will be assessed with a cotton swab (standard of care) and rated on a Likert scale of 0-10. This data will be added to the thermographic map.
- C. Comparative analysis of the two measures will be performed (separate from visit). Patient demographic and health data (see table below) will be collected by direct participant interview and review of the patient's chart in Allscripts.

12.2 Describe what data will be collected.

NOTE: For studies with multiple data collection points or long-term follow up, consider the addition of a schedule or table in your response.

Response:

Patient Name

DOB

MR#

Date of Visit

Vulvar images, both plain and infrared.

Pain sensitivity data on a Likert scale of 0-10 using cotton-tipped swabs.

Status (PWD or Control)

Race

Gravida

Para

Vaginal Births

Cesarean Births

Sexually Active

Dyspareunia

Smoking

Marital Status

Education Level

Medical History

Depression

Anxiety

Fibromyalgia

Chronic Pelvic Pain

Interstitial Cystitis

Endometriosis

Irritable Bowel Syndrome

TMJ

Other

h/o yeast infections

h/o BV

h/o abuse

PWD Patients Only

Symptom Duration

Pain Map Score

Pain Diary Score

FSDS

Previous Rx (Y/N)

Previous Rx (type)

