19.0 Data Management and Analysis*

19.1 *Describe the data analysis plan, including any statistical procedures. This section applies to both quantitative and qualitative analysis.*

Response: Both visible and infrared images will be acquired using our state-of-the-art FLIR E-95 camera. The E-95 is one of the best IR cameras available. It has very high spatial resolution and temperature sensitivity. In summation: if there is any correlation between temperature and vulvodynia, this camera will be able to see it. The camera's software stores both of these images along with metadata in a single jpeg. We have already designed our own custom software to extract the raw temperature data from these files. Our software will control the camera remotely through a USB link. This, along with mounting the camera on a tripod, will ensure that there is minimal "smearing" of the image due to small uncontrollable movements of the person operating the camera. This will give us the highest accuracy possible. In addition, our graphical software interface will allow the user to mark the image to indicate where sensitivity to pressure or an increase in thermal activity was observed. As we expect spatial variation in temperature from the affected area to the unaffected, we will provide the user with a variety of options for subtracting the average body temperature to make the difference more visible. All data will be stored securely to maintain patient confidentiality. Once we have collected enough data, we can begin the process of establishing the metrics by which we can diagnose the patients. Considering all of our data (pressure, temperature, color (from visible light image)) we can determine the connection of each to a positive diagnosis and assign a finally probability to our result.

19.2 *If applicable, provide a power analysis.*

NOTE: This may not apply to certain types of studies, including chart/records reviews, survey studies, or observational studies. This question is asked to elicit whether the investigator has an adequate sample size to achieve the study objectives and justify a conclusion.

Response: This is a pilot study. No power analysis will be performed.

19.3 *Describe any procedures that will be used for quality control of collected data.*

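### The case-control temperature comparison has no provision for matching or covariate adjustment, so a difference may reflect age or smoking, both of which are collected

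*Combined protocol and SAP*

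**What the plan says.** Section 3.1 gives one endpoint, a between-group contrast: "Thermographic evidence of inflammation in the areas of pain sensitivity in women with provoked vulvodynia compared to normal controls". The hypothesis in section 2.2 is the same kind of comparison. The Study Summary sets the size at "60 women (30 in each group"), and section 19.2 adds: "This is a pilot study. No power analysis will be performed".

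The groups enter by different routes. Under section 11.1 the investigator approaches cases when they come to the clinical suite because of vulvar pain. For controls, "Women will be approached by their own provider prior to routine annual exam". Section 5.1 states that "Control subjects will be unaffected women presenting for routine care", without vulvar pain or another active vulvar or vaginal disorder. Section 8 sets a lower age limit only. Section 7.3 says that the practice "sees 50-70 women per week for routine gynecologic care" and that only a small fraction of these women is needed.

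Section 12.2 lists date of birth, gravida, para, "Vaginal Births", cesarean births and smoking among the items for all participants, ahead of a separate block for affected women only. The analysis plan in section 19.1 names pressure, temperature and color. Taking these together, it says "we can determine the connection of each to a positive diagnosis" and assign a probability to the result. It names no test, model or covariate. The other stated uses of background data are to correlate pain maps with co-morbidities (Study Summary) and database patterns with clinical outcome data (section 2.1). Neither adjusts the case-control comparison.

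**The concern.** Without randomisation, nothing makes women who attend for vulvar pain similar in age or smoking to women who attend for an annual exam. If such a variable differs between the groups and is also related to vulvar temperature, it produces a temperature difference unconnected with vulvodynia, or hides a real one. Section 19.1 goes on to build diagnostic metrics from these data, so a confounded contrast would carry over into the diagnostic rule. Matching can be arranged only while controls are being recruited. Adjustment can be done later, but covariates chosen after the data are seen leave room for selection in a study of 60 women.

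**Working it through.** **The plan's own figure.** 30 + 30 = 60, which agrees with section 7.1. No power, significance level, effect size or standard deviation is stated, so there is nothing further to reproduce.

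**Inputs from the documents.** 30 per group; 50-70 routine patients a week (section 7.3); two years of enrolment (section 13.1).

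**Assumed inputs.** A two-sided 5% comparison of means; an age gap between groups of D standard deviations; a within-group correlation r between age and the temperature measure; no true case-control difference. The plan contains no such test, and the documents give neither D nor r.

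**Spurious shift and false-positive rate**
- Shift = r × D, in SD units.
- Standard error of the group difference = √(2/30) = 0.258 SD.
- Rejection rate = Φ(rD/SE − 1.96) + Φ(−rD/SE − 1.96).
- For D = 1 and r = 0.3, the shift is 0.30 SD and 0.30/0.258 = 1.16. The rate is Φ(−0.80) + Φ(−3.12) ≈ 0.213. The t-test version gives 0.208. Both round to 21%.

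| D | r | Shift (SD) | Rate, normal formula |
|---|---|---|---|
| any | 0 | 0 | 5% |
| 0.5 | 0.2 | 0.10 | 7% |
| 0.5 | 0.3 | 0.15 | 9% |
| 0.8 | 0.3 | 0.24 | 15% |
| 1.0 | 0.3 | 0.30 | 21% |
| 1.0 | 0.5 | 0.50 | 49% |

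The last row needs both upper extremes at once; the t-test version of it is 48%. If either D or r is zero, there is no bias.

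**Does adjustment work at this size?** In 4,000 simulated studies per setting, the unadjusted false-positive rate was 14% (D = 0.8, r = 0.3) and 47% (D = 1, r = 0.5). A linear model with the confounder and two further covariates brought both to about 5%.

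**Price of adjustment**
- The standard error is multiplied by about √((1 − r²)(1 + D²/4)).
- For D = 1 and r = 0.3 this is √(0.91 × 1.25) = √1.1375 = 1.07, so the SE is about 7% larger. The effective size is 30/1.1375 ≈ 26 per group.
- The difference detectable with 80% power moves from (1.96 + 0.84) × 0.258 = 0.72 SD to 0.77 SD.
- If matching brings D close to 0, the factor is √0.91 = 0.95 and the cost disappears.
- Age and smoking use 2 of the 58 residual degrees of freedom.

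**Feasibility of matching.** Two years is about 104 weeks: 50 × 104 = 5,200 and 70 × 104 = 7,280 routine attendances, for 30 control places. Some women will attend more than once, but the margin is wide.

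**The case against.** The strongest reply has four parts.

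1. **The plan already contains mitigation.** Sections 8.2 and 19.3 exclude pregnancy, other vulvar or vaginal disorders, and pre-existing conditions that may affect the outcome. Section 19.1 offers subtraction of body temperature, and a contrast within each woman would remove differences in overall temperature. This stands in part. The subtraction is an option left to the user and would not remove local differences related to age. The section 19.3 exclusion is unspecific, and no exclusion balances age or smoking.

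2. **The size is hypothetical.** This stands. No section links age or smoking to vulvar temperature or shows that the groups differ on them. The rates above illustrate a mechanism for a test that the plan does not specify.

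3. **It is a pilot aimed at pain maps.** Pilot status is the stated reason for having no power analysis. It does not remove bias from the stated endpoint.

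4. **Adjustment can do harm.** This stands for vaginal births. Section 4.1 says that provoked vestibulodynia interferes with sexual function, so births may partly be a consequence of the condition, and adjusting for them could remove real signal.

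A reader might also infer three stronger points that the documents do not support. Section 19.1 does not say that each measure is related to diagnosis in isolation; the sentence begins by considering all the data together. The documents do not place cases in a separate pain clinic: section 14.1 names one Obstetrics and Gynecology suite for data acquisition, so the groups differ by reason for visit and by who approaches them, not demonstrably by site. Nor does the plan rule out matching or adjustment; it is silent on both.

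**Conclusion.** The point holds as a gap in design and analysis. The stated endpoint is a non-randomised comparison of two differently recruited groups, and the plan makes no provision for matching or adjustment although the data for it are collected. A temperature difference may therefore reflect age or smoking. It would go too far to say that it will, or to quote a false-positive rate as a property of this trial: the 21% rests wholly on an assumed 1 SD age gap, an assumed correlation of 0.3 and an assumed t-test. The true bias could be near zero or larger than this. This is a cheap improvement, and the matching part has to be decided while controls can still be selected.

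**What to change.** **Section 11.1.** Fill the 30 control places by frequency match to the cases on age band, updating the number wanted in each band as cases accrue.

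**Section 19.1.** Define one temperature contrast per woman, computed in the same way in both groups. Report the group difference from a linear model with group, age (from date of birth and visit date) and smoking, with a confidence interval, alongside the unadjusted estimate. Keep age in the model after matching. Add vaginal births only in a sensitivity analysis. Tabulate age, smoking and births by group.

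**Cost.** No new data are needed. Control recruitment will be slightly slower. Adjustment is inexpensive but not free: the SE is about 7% larger if age still differs by 1 SD with r = 0.3, a cost that age matching largely removes. The model cannot be finalised until the temperature contrast is defined, so the two changes belong in the same amendment.
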